## 9.10. Safety Evaluation

Adverse Event (AE) information will be collected by the site from subject enrollment (consent) through study termination. AEs will be followed until the event has resolved (in the case of permanent impairment, the event will be followed until it stabilizes, and the overall clinical outcome has been ascertained).

The Investigator will report any adverse events that may occur to the Sponsor, and will assess seriousness, relationship (to the device, procedure and renal denervation therapy where applicable), subsequent intervention required, resolution status and whether or not the adverse event resulted in the subject's discontinuation from the study. The Investigator will provide further information regarding adverse events as requested by the Sponsor.

## 9.11. Subgroup Analyses

Analysis will be carried out for the following subgroups to assess consistency of results.

- Gender
- Age at baseline <65 vs. ≥ 65 (years)

- BMI by tertiles (kg/m^2)
- Type 2 diabetics vs. non-diabetics
- Current smokers vs. non-smokers
- Baseline eGFR < 60 vs. ≥ 60 (mL/min/1.73 m²)

- Obstructive sleep apnea yes vs. no
- US vs. OUS Subjects
- US African American vs. US Non African American subjects
- European vs. Japanese vs. Australian subjects
- Baseline ambulatory SBP by tertiles and medians (mmHg)

- Baseline office SBP by tertiles and medians (mmHg)
- Baseline ambulatory heart rate by tertiles and medians (bpm)
- Baseline office heart rate by tertiles and medians (bpm)
- 24-Hour Pulse Pressure <60 vs. >= 60 mmHg (mmHg)
- Orthostatic Hypertension at baseline
- Orthostatic Tachycardia at baseline
- Plasma Renin Activity at baseline <0.65 vs. ≥0.65 (ng/mL/h)

- Aldosterone Renin Ratio at baseline by tertiles
- Aldosterone at baseline by tertiles (ng/dL)
- Tertile analysis by total number of ablations performed
- Tertile analysis by total number of ablations performed in branch vessels
- Tertile analysis by total number of ablations performed in main renal artery vessels
- Tertile analysis by total number of 45 second ablations performed
- Medication adherent vs. non-adherent subjects at screening visit 2 (SV2) and 3 months (from urine and serum tests)

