  - **Renin and Aldosterone (blood):** Samples should be collected in the morning after the patient has been out of bed for  $\geq 2$  hours and after resting quietly sitting for a minimum of 5 minutes but preferably 30 minutes. The time of day and subject's position (standing, sitting, or lying down) when the blood sample is collected should be documented and the same time of day ( $\pm 2$  hours) and subject position should be used for collection of blood samples for determination of renin and aldosterone at later time points in the study.
  - **Drug testing (urine/blood)** to ensure medications are no longer present in the subject's system. A urine sample will be collected, preferably using the subject's first morning urine. A blood sample will be collected at the time of the visit.
- f. **24-hour Ambulatory Blood Pressure Monitoring** will be applied at the conclusion of Screening Visit 2 to confirm subject's baseline blood pressure. This value will be utilized as the baseline value for calculating change in 24-hour ABPM at various time points post-procedure. Subjects with a 24-hour systolic ABPM of  $< 140$  or  $\geq 170$  mmHg after completion of the screening visit will be exited from the study. Subjects with a 24-hr systolic ABPM of  $\geq 140$  and  $< 170$  mmHg are eligible to continue to the randomization (procedure or control) visit. A single repeat measurement is allowed in case of the following: 1.) a technical issue with the blood pressure monitor or failure to follow ABPM instructions, or 2.) if a valid number of readings is not obtained, or 3.) if the 24-hr systolic ABPM measured

135 - <140 mmHg or 170-175 mmHg. ABPM must be conducted according to the guidelines in Appendix L.7. If ABPM is repeated office blood pressure and drug testing must be repeated on day the ABPM is applied.

- g. **Adverse Event Reviews** will be completed to document adverse events that occur after enrollment.
- h. **Baseline Renal Imaging** Submit a baseline Duplex Ultrasound, CT, or MRA if obtained per standard of care prior to procedure within one year from the date of the screening visit 1 and upload via Intelemage or send via courier.

Subjects determined to not be eligible for randomization will be exited from the study, as described in the Subject Exit from Study section of this Clinical Investigation Plan.

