- b) **SF-36:** The 36-Item Short Form Survey (SF-36) will be administered at the 3, 6, 12, 24 and 36 month post-procedure visits to measure health outcomes.
- c) **Clinical Assessment** will be conducted at all post-procedure follow-up visits to evaluate the subject's current medical condition. An individual experienced in performing histories and physical exams is required to assess subjects for safety assessment during the period of time that study subjects are not on antihypertensive medications.
- d) **Office Blood Pressure** measurements will be obtained in accordance with Appendix L.7 at all post-procedure follow-up visits.
- e) **Laboratory Tests:**
  - **Basic metabolic panel Chem-7 (blood):** serum-creatinine, sodium, potassium, blood urea nitrogen (BUN), bicarbonate, chloride and glucose. Bicarbonate will not be measured for subjects enrolled in Japan and Europe.
  - **eGFR** will be calculated from the serum-creatinine in the Chem-7 panel for eligibility criteria by using the 4 variable Modification of Diet in Renal Disease (MDRD) Formula or the local Japanese criteria for subjects enrolled in Japan.
  - **Renin and Aldosterone testing (blood; 3 month follow-up only)** Samples should be collected in the morning after the patient has been out of bed for  $\geq 2$  hours and after resting quietly after a minimum of 5 minutes but preferably 30 minutes. The time of day and subject's position (standing, sitting, or lying down) before the blood sample is collected should be documented and the same time of day ( $\pm 2$  hours) and subject position should be used for collection of blood samples for determination of renin and aldosterone at later time points in the study.
  - **Drug testing (urine/blood)** to ensure no medications are present in the subject's system at 3 months follow-up and to ensure that prescribed medications are in the subject's system at 6, 12, 24, and 36 months. A

urine sample will be collected, preferably using the subject's first morning urine. A blood sample will be collected at the time of the visit.

- f) **Initiate Medication Re-Introduction for Subjects with Systolic OBP  $\geq$  140 mmHg at 3M follow-up visit.** Starting at 3 month follow-up after clinical assessment and a valid ABPM are completed.
- g) **Medication & Adverse Event Reviews** will be completed at each follow-up visit to assess any changes in medication usage or medical condition:

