### F.8 Escape Medication Protocol during Off Medication Period

In the event a subject's office SBP  $\geq 180$  mmHg or there is a safety concern, from randomization up to and including the 3 month visit, the subject will be seen a second time within 72 hours for a repeat office BP. If the subject's office SBP remains  $\geq 180$  mmHg, the subject will be put back on an antihypertensive medication regimen per the investigator's discretion. All efforts should be made to obtain an ABPM and Chem 7 panel, and urine and blood for antihypertensive drug testing, prior to the subject being put back on medications. If the subject already started medications, the subject and investigator should consider if it is safe to take the subject off medications for 2 weeks in order to obtain the requirements at the 3 month visit to ensure endpoint data is collected. The subject will be exited from the off medications portion of the study and will be followed according to Table 6. If the subject's office SBP  $< 180$  mmHg, the subject will continue to be followed per Table 4. At any time while the subject is not taking antihypertensive medications, either the subject or the investigator may restart antihypertensive medications if there is a safety concern and the subject will be followed according to Table 8. All blood pressures must be taken according to the guidelines in Appendix L.7 with the exception of needing to be completed by 10:30 am. Visits for monitoring the subject's BP for these purposes must be documented on the eCRF. Escape subjects randomized to the Control (sham) group may be offered renal denervation therapy (crossover) after their 6- month follow-up visit. Refer to Section F.10 for crossover procedures.

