#### 9.1.3. Analysis Sets

#### 9.1.3.1. Intention-To-Treat (ITT) Population

This is the primary analysis set for efficacy and safety evaluation and consists of all randomized subjects, analyzed according to their randomized treatment. Subjects who meet the anti-hypertensive medication escape criteria (OSBP>180 mmHg or safety reasons) will be analyzed using Last Observation Carried Forward (LOCF) for their blood pressure measurements out to 3 months. Safety outcomes, and office and ambulatory blood pressure outcomes at each follow-up visit will be presented for this population.

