#### 9.9.9. Additional Objectives

The following additional analyses will be conducted:

- Quality of Life (QOL) measures (EQ5D and SF36).
- Antihypertensive medication usage through 36 months.
- Additional procedural characteristics e.g. treatment duration, frequency of distal renal artery treatment, ablations per vessel, location of ablations, number of ablations per patient and other characteristics will be analyzed to assess their impact on blood pressure.
- Medication adherence will be assessed using results from drug testing. In addition, we will perform analyses to evaluate the effect of medication adherence on blood pressure change.
- Analyses looking at long term imaging will be performed.

RDN vs. control groups will be compared out to 6-months post randomization, prior to the crossover procedure. Statistical comparisons will be performed using the independent samples t-test for continuous endpoints and Fisher's exact test for categorical endpoints. In addition, two-sided 95% confidence intervals of the difference between RDN and control groups will be presented.

RDN vs. Crossover vs. Non-Crossover groups will be compared out to 36 months post-procedure for the RDN and Non-Crossover groups and out to 24 months for the Crossover group using chi-square tests for categorical data and ANOVA for continuous data.

Changes in blood pressure measurements from baseline to follow-up within each group will be assessed using paired t-tests. Two-sided 95% confidence intervals of the mean change from baseline will also be presented for each group.

These additional analyses will be presented for the ITT study population defined in section 9.1.3.1.

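### Three-month drug-test status is a post-randomization variable: it should not be a consistency subgroup, and an adherence 'effect' estimated from it would be confounded by indication

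*SAP*

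**What the plan says.** SAP 9.11 introduces its list with "Analysis will be carried out for the following subgroups to assess consistency of results". Most entries are baseline factors. The last is "Medication adherent vs. non-adherent subjects at screening visit 2 (SV2) and 3 months", determined from urine and serum. Protocol H.9 carries the same entry.

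The two visits differ in kind. At SV2 (Protocol F.5) the test is done "to ensure medications are no longer present in the subject's system", before randomization. At 3 months (Protocol F.7) it is done "to ensure no medications are present in the subject's system at 3 months follow-up", after randomization and treatment.

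SAP 9.9.9 assesses adherence from drug testing and adds that "we will perform analyses to evaluate the effect of medication adherence on blood pressure change". It names no visit, model, adjustment or estimand for this.

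Protocol F.8 sets out how drugs may be restarted in the off-medication period. If office SBP is still at or above 180 mmHg on repeat, "the subject will be put back on an antihypertensive medication regimen per the investigator's discretion". Also, "either the subject or the investigator may restart antihypertensive medications if there is a safety concern". Under SAP 9.1.3.1 these escape subjects "will be analyzed using Last Observation Carried Forward (LOCF) for their blood pressure measurements out to 3 months".

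**The concern.** A consistency subgroup asks whether the treatment effect is similar across kinds of patient, so the strata must be fixed before treatment. Three-month drug status is not. During the off-drug period a positive test means that an antihypertensive was taken, and a subject with higher pressure has more reason to take one. If denervation lowers pressure, status is affected by both treatment and outcome, and the arms within a stratum are no longer a randomized comparison.

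The adherence 'effect' has a related and potentially larger problem. If people who take drugs do so because their pressure is high, comparing them with people who do not mixes the drug's lowering effect with the higher pressure that prompted it. The result can show drug-takers with equal or higher pressure.

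This matters because the protocol names uncontrolled adherence as a possible confounder in the previous sham-controlled trial (B.1.2, Clinical Summary) and uses it to justify the washout design (B.3). Readers will look to the adherence analysis for reassurance, and a null or reversed 'effect' could be taken to mean that undeclared drug use did not matter.

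**Working it through.** **The plan's own figures.** Neither document gives a figure for adherence. As a check on the design inputs, a simulation of the discount-function design (known-SD approximation) gave 92.4 to 92.8% success on the primary endpoint and 90.6 to 91.8% on both endpoints. SAP Table 5 states 94%.

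**Inputs from the documents.** 24-hour SBP change is -4.74 (RDN) and -0.74 (control), SD 12, difference -4.0 (SAP Table 3). Allocation is 1:1, with 210 to 300 evaluable subjects.

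**Assumptions not in the documents.** The true RDN effect is -4.0 in everyone. Between 5 and 20% are drug-positive at 3 months. The drug lowers SBP by D = 5 mmHg (10 as an alternative). The odds ratio (OR) for drug use is 1.0 to 2.5 per 10 mmHg higher off-drug SBP.

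**Adherence 'effect'.** Within an arm let Y be the off-drug change, with variance σ² = 144, and let logit p = a + bY with b = ln(OR)/10. Let q be the share positive. Then

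E[Y | positive] - E[Y | negative] = bσ² × E[p(1-p)] / {q(1-q)}.

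The last ratio is at most 1, so bσ² is an upper bound on the bias. For OR 1.25, ln(1.25)/10 × 144 = 3.2 mmHg; for OR 2.0, ln(2)/10 × 144 = 10.0. The estimated contrast is -D plus the bias. With 10% positive and D = 5:

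| OR per 10 mmHg | Upper bound bσ² | Bias | Contrast (truth -5) | Wrong sign, N=210 |
|---|---|---|---|---|
| 1.0 | 0 | 0 | -5.0 | 4% |
| 1.25 | 3.2 | 3.2 | -1.8 | not run |
| 1.3 | 3.8 | 3.7 | -1.3 | 32% |
| 1.6 | 6.8 | 6.6 | +1.6 | 72% |
| 2.0 | 10.0 | 9.3 | +4.3 | 94% |

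Setting bσ² = 5 gives OR = exp(50/144) = 1.42, so the mean sign changes at an OR slightly above that. With D = 10 the mean contrast is still about -0.7 at OR 2.0 and reverses only at OR 2.5 (+1.7).

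**RDN effect within strata (truth -4.0).**
- Same logistic mechanism in both arms: -3.5 to -4.0 among drug-negative and -3.3 to -4.1 among drug-positive subjects.
- Noisy pressure threshold: -2.3 to -3.8 among drug-positive.
- Hard threshold: -0.5 to -0.9 among drug-positive and -2.3 to -3.3 among drug-negative.
- Selection differing by arm (OR 2.0 in RDN, 1.3 in control): +0.4 to +1.6 among drug-positive.

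**Precision.** With 10% positive, the RDN effect in that stratum has SE 12 × √(2/10.5) = 5.2 mmHg at N = 210 and 12 × √(2/15) = 4.4 at N = 300. Even with no bias, a true -4 would show the wrong sign with probability Φ(-4/5.24) = 0.22 at N = 210.

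**The case against.** The strongest reply has five parts.

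- **The dependence on pressure is not shown for the subjects who matter.** The documented pressure-triggered route is escape. Escape subjects move to Protocol Tables 3 and 6, which list no 3-month drug test or ABPM, and F.8 asks for samples before drugs restart. That route should feed few subjects into the 3-month drug-positive group. For undeclared use, no link with pressure is documented. This stands: the dependence is plausible but not established, and its strength is assumed.
- **SAP 9.9.9 names no visit.** From 6 months the test checks that prescribed drugs are present, so the off-drug mechanism does not apply there. This also stands, and the bias figures are conditional on 3-month status being used. Later status would still be observational, because prescribing after 3 months depends on office SBP (Protocol F.9).
- **By-arm reporting is already implied.** SAP 9.9.9 compares RDN with control to 6 months, with Fisher's exact test and 95% confidence intervals. This stands, and that comparison need not be added.
- **Imputation is weak for the primary endpoint.** No scheduled post-procedure ABPM precedes 3 months, and if drug use follows off-drug pressure the values are not missing at random. This stands and shapes the fix.
- **The 3-month results are already public** (Protocol B.1.2), so deleting a listed subgroup would itself be post hoc. This supports relabelling the split as descriptive rather than suppressing it.

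A reader might infer that the RDN effect in the 3-month subgroup is itself off by several mmHg or reversed. The documents do not support that. Distortion of that size needs a sharp threshold, and reversal in expectation needs selection that differs by arm; neither document describes either for the subjects tested at 3 months.

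**Conclusion.** The point holds in a limited form. Three-month drug-test status is measured after randomization, can depend on blood pressure, and does not belong beside baseline factors as a test of consistency. The expected distortion of the within-stratum RDN effect is mostly under 1 mmHg, and in the small drug-positive stratum it is dwarfed by the standard error of 4 to 5 mmHg.

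The larger exposure is the SAP 9.9.9 'effect'. If it is estimated from 3-month status, confounding by indication would bias a true -5 mmHg drug effect by about 3 to 9 mmHg for odds ratios of 1.25 to 2.0 per 10 mmHg, with possible sign reversal. At 1.25 the mean sign is still correct, and with no link to pressure the bias is zero. These odds ratios, the drug effect and the drug-positive share are assumptions.

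Nothing here bears on the trial's success criteria: both powered efficacy endpoints are analysed by intention to treat without this variable. The SV2 half of the subgroup is unaffected. The per-protocol set (SAP 9.1.3.3) conditions on the same 3-month test and needs the same caution in reading.

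**What to change.** 1. In SAP 9.11 and Protocol H.9, keep only SV2 drug-test status as a consistency subgroup. Show any 3-month split separately, labelled descriptive and non-randomized.
2. Keep the by-arm comparison of 3-month drug detection that SAP 9.9.9 already implies, and state how escape subjects are classified, which neither document does.
3. Replace the adherence 'effect' in SAP 9.9.9 with a sensitivity analysis of both powered endpoints. Keep every subject in the randomized arm and set drug-positive 3-month values to missing. Impute them by extending the SAP 9.4 multiple imputation, which already uses baseline SBP, treatment group, age, gender and BMI, with the off-drug office readings at weeks 2, 4 and 8 and any ABPM taken before drugs were restarted.
4. Add a delta-adjusted version in which the imputed off-drug SBP is higher than the model predicts. A range of 0 to 10 mmHg would cover the 3 to 9 mmHg above. It is needed because the values may not be missing at random and, for the primary endpoint, no scheduled post-procedure ABPM precedes 3 months.

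The cost is SAP and protocol wording, one additional sensitivity run on data already collected, and the loss of the 3-month adherence row from the subgroup display. The analysis will not fully remove the selection; the delta range shows how much it could matter.

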## 9.12. COVID-19 Related Analyses

In accordance with FDA guidance document "FDA Guidance on Conduct of Clinical Trials of Medical Products during COVID-19 Pandemic" [8], we will provide COVID-19 related protocol deviation tables and AE/SAE tables summarizing the site-reported adverse events attributed to COVID-19.

## 9.13. Changes to Planned Analysis

There are no changes to the planned analysis at this time.

# 10. Validation Requirements

Statistical programming for the analysis datasets, primary endpoints, secondary safety endpoints, and secondary effectiveness endpoints require Level 1 (independent) validation. Other objectives and subgroup analyses require Level 1 (independent) or Level 2 (Peer review) validation.

# 12. Statistical Appendices

# 12.1. Appendix I: Imputation of Missing Dates

# **Imputation of Missing AE Onset Date**

Valid Portion	Missing Portion	Imputed Value for Missing Portion
Month, Year	Day	Set Day = first day of that month and year, then set the day = later of (New onset date, informed consent date).
Year	Day, Month	Set date = later of (January 1st of that year, informed consent date).
None	Day, Month, Year	Informed consent date.

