**Clinical Procedures**

**Table 1: Schedule of Testing for All Subjects (See Table 2 for Crossover Subjects' Testing)**

3 Months (90 days): 76-104 days - 4 Months (120 days):113 -127 days - 6 Months (180 days): 166-194 days - 12 Months (360 days): 330-390 days - 24 Months (720 days): 690-750 days - 36 Months (1080 days): 1050-1110 days

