## F.16 Adverse events and device deficiencies

### F.16.1 Definition/classification

For each reported adverse event, the Investigator will assess the events in terms of relationship to the device, relationship to the procedure, relationship to the renal denervation therapy (if applicable) as defined below.

- **Device:** A device related AE is defined as any AE for which a causal relationship between the event and the Symplicity Spyral™ catheter or Symplicity G3™ generator can be established.
- **Procedure:** A procedure related AE is defined as any AE occurring within 7 days post-procedure (or post-denervation in the case of a control group subject being denervated at cross over) associated with the renal angiogram and intervention techniques involved in preparing for the actual renal denervation treatment.
- **Therapy:** A therapy related AE is defined as any AE associated with a subject's physiological response to the renal denervation procedure.

For the purposes of the clinical report, Medtronic will classify each Adverse Event according to the latest version of International Organization of Standardization (ISO) ISO 14155.

Where the definition indicates "device", it refers to any device used in the study. This might be the device under investigation, or any market released component of the system.

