#### **Powered Primary Safety Endpoint**

Incidence of Major Adverse Events (MAE), defined as a composite of the following events, through one-month post-randomization (6 months for new renal artery stenosis)

- All-cause mortality
- End Stage Renal Disease (ESRD)
- Significant embolic event resulting in end-organ damage
- Renal artery perforation requiring intervention
- Renal artery dissection requiring intervention
- Vascular complications
- Hospitalization for hypertensive crisis not related to confirmed non-adherence with medications or the protocol
- New renal artery stenosis > 70%, confirmed by angiography and as determined by the angiographic core laboratory

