#### 9.1.4. Crossover Procedures

Control subjects may crossover and receive renal denervation therapy at or after their 6 month follow-up visit. For the subjects who had already completed their 6 month visit, the decision to crossover must take place at their next in person visit. All subjects will have 30 days from the Crossover visit (6, 12, 24, 36 month follow-up or Unscheduled visit) to undergo the crossover procedure. Subjects who are more than 30 days from their 6, 12, 24 or 36 month, must complete a crossover Baseline visit prior to crossing over. Control subjects who are coming in for their scheduled 6, 12, 24 and 36 month follow-up visit do not need to come in for a crossover Baseline visit if all the required crossover Baseline procedures occurred, including lipid panel, hs-crp and uric acid blood tests. To crossover, the subject cannot meet any of the anatomical and glomerular filtration rate (eGFR) exclusion criteria, and cannot be pregnant, nursing or planning to become pregnant during the course of the study follow-up. Crossover subjects will undergo follow-up visits at 1, 3, and 6 months ( $\pm$  14 days) and annually at 12 and 24 months ( $\pm$  30 days) post-procedure.

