**Table 2: Study Sources of Patients for Primary Safety Endpoint Data** 

Study
SPYRAL HTN-OFF MED prior data (First 80
Subjects)
Randomized 1:1 to RDN:CONTROL
SPYRAL PIVOTAL – SPYRAL HTN-OFF MED
Randomized 1:1 to RDN:CONTROL
SPYRAL HTN-ON MED First 106
Randomized 1:1 to RDN:CONTROL
SPYRAL HTN ON MED Extension
Randomized 2:1 to RDN:CONTROL
SPYRAL HTN-OFF MED Crossovers (from
prior and pivotal)
SPYRAL HTN-ON MED Crossovers (from first
106 and Extension subjects)

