All the safety endpoints will be adjudicated by the Clinical Events Committee (CEC). The following algorithm will be used to evaluate the safety event rates: The denominator will include all subjects who either had a CEC adjudicated event prior to the time of interest (180 days for 6 months events, for example), or had last contact date that is beyond the lower window of the follow up (166 days for 6 month events, for example). The numerator will include all subjects who had CEC adjudicated events up to the time of interest (180 days for 6 months events, for example).

The secondary safety endpoints, out to 6-months follow-up, will be compared between treatment groups using Fisher's exact test. Two-sided 95% confidence intervals of the difference between treatment groups will also be presented.

After 6-months follow-up, control subjects may crossover (undergo renal denervation), and secondary safety endpoints will be summarized by group (RDN, Crossovers, Non-Crossovers). RDN vs. Crossover vs. Non-Crossover groups will be compared out to 36 months post-procedure for the RDN and Non-Crossover groups and out to 24 months for the Crossover group using chi-square tests for categorical data and ANOVA for continuous data.

The secondary safety analyses will be performed using the ITT population defined in section 9.1.3.1.

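### Does flooring an imputed adverse-event onset only at consent misplace safety events around the index or crossover procedure?

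*SAP*

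**What the plan says.** SAP Appendix I (12.1) treats a missing onset day thus: "Set Day = first day of that month and year, then set the day = later of (New onset date, informed consent date". Year-only dates go to 1 January with the same floor, and wholly missing dates go to consent. No randomization, procedure or crossover date enters the rule.

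The SAP 9.9.2 counting rule reads: "The numerator will include all subjects who had CEC adjudicated events up to the time of interest". Protocol H.3 has the same rule. Both give 180 days for a 6-month event and use day 166 for the denominator. Neither sets a lower limit on the event date. The headings in 9.9.2 do name anchors: post-procedure for the acute endpoints and post-randomization for the chronic ones. The randomized comparison is limited in time: "The secondary safety endpoints, out to 6-months follow-up, will be compared between treatment groups". Later results are grouped by subject as RDN, crossover or non-crossover.

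The primary safety window runs "through one-month post-randomization (6 months for new renal artery stenosis". SAP Table 2 lists "SPYRAL HTN-OFF MED Crossovers" among the sources for the 253 subjects. Crossover happens at or after the 6-month visit ("6 Months (180 days): 166-194 days" in Protocol Table 1), and under SAP 9.1.4 "All subjects will have 30 days from the Crossover visit".

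**The concern.** Consent is too early to act as a useful floor. A site that knows only the month of an event will often have it imputed to a date before the treatment that may have caused it. The days just after a procedure are affected most. Protocol F.16.1 also builds a time limit into causality: "A procedure related AE is defined as any AE occurring within 7 days post-procedure".

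Three things could be at stake:

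- A programmer who reads the post-randomization or post-procedure labels as a day-0 start would discard back-dated events.
- An event after a control subject's crossover could be dated on or before day 180 and be charged to sham in the 6-month comparison.
- In the primary safety pool, a window counted from randomization has closed before any crossover takes place. Some other origin is needed, and the SAP does not write it down.

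Appendix I also sets partial medication stop dates early, which could show a drug as stopped at a visit when it was still being taken.

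**Working it through.** **Inputs.** Consent precedes Screening Visit 1 (Protocol F.1). Screening Visit 2 follows in 3-4 weeks, and the procedure within 14 days after that (Protocol F.5). Consent is therefore about 21 to 28 + 14 = 42 days before the index procedure. Crossover is at or after the 6-month visit, day 166 at the earliest, with 30 days allowed. Adverse events are collected from consent onwards (SAP 9.10).

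**1. The rule does pre-date events.** Imputed onset = max(first of month, consent). Example with assumed dates: consent 10 May, procedure 20 June, onset known only as June. The imputed date is 1 June, 19 days before the procedure. Among procedure-month onsets, this happens unless the procedure falls on the 1st: 365 - 12 = 353 of 365 dates, or 96.7%.

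I simulated 400,000 patients with procedure dates uniform over three years, the gaps above, and onsets uniform over the stated range with the day missing.

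| True onset after index procedure | Dated before it |
|---|---|
| Days 0-7 | 85% |
| Days 0-30 | 48% |
| Days 0-90 | 16% |

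**2. The written counting rule loses none of them.** The first of the month is not later than the true date. Consent is not later either, because collection starts there. So imputed date ≤ true date. If the true date is at or before the cutoff, so is the imputed date, and the event stays in the numerator. The rule can only add events: 49% of day-missing events truly on days 31-60 are pulled into a 30-day window, which overstates early harm. The table above becomes a loss only if someone adds a day-0 filter that the plan does not contain.

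**3. Index day 0.** Angiography and randomization take place at one visit (Protocol F.6), so post-procedure and post-randomization are effectively the same clock.

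**4. Crossover, 6-month comparison.** Crossover is taken as day 166-194 plus 0-30 days, with events on days 0-30 after it and the day missing. The middle column imputes the crossover date when the month matches.

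| | Current rule | Re-dated to crossover procedure | True dates |
|---|---|---|---|
| Dated before crossover procedure | 47% | 0% | 0% |
| On or before day 180 from index | 21% | 8.5% | 2.4% |
| On or before day 180, crossover after day 180 | 14% | 0% | 0% |

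The same re-dating acts on genuine sham-period events. Take day-missing events in the 30 days before crossover that truly fell by day 180. About 24% would move past day 180 and leave the control numerator, against 0% now. Over all day-missing sham events to day 180 this is about 2%.

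**5. Crossover, primary safety pool.** With one month taken as 30 days, a window counted from randomization ends 166 - 30 = 136 days before the earliest crossover. A crossover subject can contribute post-denervation events only if the clock starts at the crossover procedure. No other reading gives a usable window.

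**6. The decision limit.** 11/253 = 4.35%, with an exact one-sided 95% upper bound of 7.094%. This reproduces the SAP's 4.3% and 7.09%. 12/253 gives 7.57% and fails. The documents give no count of partly dated events, so no shift against this limit can be calculated.

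**The case for a change.** The best case for a change is that it is cheap. SAP section 10 requires independent programming of the safety endpoints, and two programmers could place the same event differently. SAP 9.9.2 uses post-randomization in the chronic heading and post-procedure in the later text. It gives no start date for the crossover group, although crossovers can enter the primary safety set. If a lower limit is added to keep a crossover subject's sham-period events out of that set, back-dated post-crossover events would go with them.

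The missing crossover day 0 stands as a gap in the text. It has one workable answer, and independent validation would bring any disagreement to light. The loss of back-dated events requires an adjudicated event without a day. Sites must report the event date (Protocol F.16.2), the committee reviews source documents (Protocol F.15), queries are issued (Protocol G.1.4), and source verification of at least 90% is the aim (Protocol G.2). Death, perforation, dissection, hospitalization and angiographic stenosis normally carry a dated record. Analysts would use the adjudicated date ahead of an imputed one.

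The other two points are conditional. Procedure-relatedness is assessed by the investigator, and nothing says it is recomputed from imputed dates. Nor does SAP 9.7 say that medication use at visits is built from stop dates, and Protocol F.7 has a medication review at every visit.

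**Conclusion.** No change is needed. The mechanism is real: about 48% of day-missing onsets on days 0-30 would carry a date before the index procedure, and about 47% before the crossover procedure. Under the written counting rule no index event is lost, and 9.9.2 does name its index anchors. What is left is detail that analysts would fill sensibly: the crossover procedure is day 0 for crossovers in the safety pool, and an adjudicated date overrides an imputed one.

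Re-dating onsets to the procedure would not be a clear gain. It lowers misplacement of post-crossover events by day 180 from 21% to 8.5%, but moves 24% of the late sham-period events described above out of the control count. Nothing in the documents shows which kind is more common.

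The percentages assume uniform onsets, the protocol's visit gaps and a missing day. They are shares of partly dated events, whose number is not given and should be small for adjudicated endpoints. Protocol B.1.2 reports no major safety events at 1 month and one per group up to 3 months in the two OFF MED cohorts. No effect on the primary safety result is shown.
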